#### 8.2.2 Cytokine and Pro/Anti-Inflammatory Marker Analysis

For inflammatory cytokines, time course data will be analyzed using a GLMM to test differences across time between pre- and post-treatment. The dependent variables will be the neuroinflammatory biomarkers with time (to model the trajectory) and GOSE (3-4 or 5-8) as covariates and a random subject effect (to account for within subject correlation). Point estimates of pre- and post-treatment differences will be reported along with 95% confidence interval

#### 8.2.3 PET Imaging Analysis

PET imaging analysis: Following completion of PET scanning, two main types of PET analyses will be completed:

##### 8.2.3.1 Volume of Interest Analysis:

A hypothesis-driven VOI analysis where selected brain regions are examined will be conducted. Advantage of narrow search within regions involved in regulating the pain experience (e.g., anterior cingulate, insular cortex, nucleus accumbens, thalamus, amygdala, periaqueductal gray). Predefined VOIs obtained from data of previous studies are applied to image data and transferred to [C]ER-176 maps.

##### 8.2.3.2 Statistical Parametric Mapping:

In these types of analyses, statistical parametric maps are obtained using whole brain image subtraction routines. Differences between volunteer groups (and covariants with phenotypic data) will be compared using the general linear model on a voxel by voxel basis within SPM8 and Matlab software with correction for multiple comparisons. Resulting Z-maps of statistical significance are mapped onto stereotactic space using volunteers' anatomically standardized T1-weighted MRIs. Only gray matter pixels and regions with specific binding will be included in the statistical parametric analyses (voxels with BPND values > 0.2). To compensate for small residual anatomic variation between subjects and to improve signal to noise ratio, a 3D Gaussian filter (FWHM 6 mm) will be applied to each scan. For

each subtraction analysis, one- or two-sample t-statistic values will be calculated for each voxel using a pooled smoothed variance across voxels. Areas of significant differences will be detected with a statistical threshold set to control for a Type-I error rate at  $p = 0.05$  for multiple comparisons, estimated using the Euler characteristic based on the number of voxels in the grey matter and image smoothness. This threshold typically corresponds to  $z=4.3$  to  $4.6$ , lower for large size regions after cluster volume correction is applied. Plans for implementing corrections based on false discovery rate (FDR) are underway. The standard Euler characteristic method controls for Family-wise Type-I error, the chance of any false positives. FDR is the proportion of false positives among suprathreshold voxels. The FDR is a more lenient measure of false positives than Family-wise Error and hence more powerful, while offering a principled way to control false positives. After significant statistical effects are obtained in SPM, regional data is extracted into SPSS, plotted to assess for outliers, and used in additional analyses (i.e. correlations with dependent variables). Data is tested for normality (uniformly encountered) and if not obtained, equivalent non-parametric analyses will be used.

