We propose to investigate changes (from enrollment to 6 months post infusion) in global measures of structural integrity in GM and WM using volumetric and DT-MRI based imaging according to the protocols described in the appendix/Investigator Brochure. T1-weighted images will be reviewed for image quality prior to performing morphometric analyses. Using Freesurfer v5.0.0 software (www.surfer.nmr.mgh.harvard.edu), each brain is skull-stripped and segmented into 3 classes of voxels: gray matter, white matter, and cerebrospinal fluid (Dale & Sereno, 1993; Dale et al., 1999). Subsequently, the cortex will be parcellated for individual gyri yielding morphometric measures of cortical thickness, volume, and surface area and measures of underlying white matter fractional anisotropy (FA) within each gyrus (Fischl & Dale, 2000).

Further, we will measure white and gray matter regions of interest and will correlate the degree of injury/preservation with functional and neuropsychological outcome measures. These measures have been validated in multiple studies and are recommended by a task force from NIH and NIDRR as common data elements for TBI outcome research (McCauley et al., in press) and for use in clinical trials in TBI (Bagiella, 2011). These measures were also selected to assess relations with specific white and gray matter structures that are particularly vulnerable to disruption by TBI. White matter: corpus callosum (processing speed), corticospinal tract (motor coordination). Gray matter: frontal lobe (fluency, attention, working memory) and temporal lobe (declarative memory).

1.3 Exploratory Objectives: Investigate if HB-adMSC infusion reduces the neuroinflammatory response to injury.

Microglial activation has been shown to occur after TBI and chronic activation is associated with WM loss over time. (Loane, 2014; Ramlackhansingh, 2011). We have confirmed these findings in a rodent model of TBI as well, using both the M1 microglial activation marker, IBA-1 as well as the TSPO ligand, PBR-28. [¹¹C]ER-176 is a Radioligand for the TSPO with adequate sensitivity to robustly image all three affinity genotypes in human brain (Ikawa, 2017). We plan to use the approach to image the neuroinflammatory response to injury. These imaging findings will be correlated with circulating inflammatory cytokines.

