each subtraction analysis, one- or two-sample t-statistic values will be calculated for each voxel using a pooled smoothed variance across voxels. Areas of significant differences will be detected with a statistical threshold set to control for a Type-I error rate at $p = 0.05$ for multiple comparisons, estimated using the Euler characteristic based on the number of voxels in the grey matter and image smoothness. This threshold typically corresponds to $z=4.3$ to 4.6 , lower for large size regions after cluster volume correction is applied. Plans for implementing corrections based on false discovery rate (FDR) are underway. The standard Euler characteristic method controls for Family-wise Type-I error, the chance of any false positives. FDR is the proportion of false positives among suprathreshold voxels. The FDR is a more lenient measure of false positives than Family-wise Error and hence more powerful, while offering a principled way to control false positives. After significant statistical effects are obtained in SPM, regional data is extracted into SPSS, plotted to assess for outliers, and used in additional analyses (i.e. correlations with dependent variables). Data is tested for normality (uniformly encountered) and if not obtained, equivalent non-parametric analyses will be used.

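### SPM-stream PET values are extracted after significance and correlated in the same subjects, which can be circular; no estimate or correlation is assigned to the predefined VOIs

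*SAP*

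**What the plan says.** Section 8.2.3 (same text in SAP and Protocol) sets out two PET analyses.

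- **VOI analysis, 8.2.3.1.** "Predefined VOIs obtained from data of previous studies are applied to image data". This does not depend on any SPM result. The example regions are described as ones that regulate pain. No model, estimate, interval or correlation is given for the VOI values.
- **SPM analysis, 8.2.3.2.** "Differences between volunteer groups (and covariants with phenotypic data) will be compared using the general linear model on a voxel by voxel basis". The statistic is described as "one- or two-sample t-statistic values will be calculated for each voxel using a pooled smoothed variance across voxels". The threshold is "set to control for a Type-I error rate at $p = 0.05$ for multiple comparisons", and the text adds: "This threshold typically corresponds to $z=4.3$ to 4.6", lower for large regions after cluster correction.

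The SPM section then gives the extraction rule: "After significant statistical effects are obtained in SPM, regional data is extracted into SPSS, plotted to assess for outliers, and used in additional analyses". The use it names is "i.e. correlations with dependent variables". It describes no independent data, cross-validation, bias correction or numerical outlier rule.

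Protocol 1.3 adds, for the neuroinflammation objective: "These imaging findings will be correlated with circulating inflammatory cytokines". It sets no condition and does not say which PET values are meant. Section 8.1 promises treatment-effect estimates with 95% confidence intervals for every measure, again without naming a PET source.

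**The concern.** Choosing a region because its data cross a high threshold, and then estimating from the same data in that region, selects in favour of chance. The values that survive are those where the true effect and the noise point the same way.

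Two situations need to be kept apart:

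- The SPM contrast is a regression on a phenotype, and the extracted cluster is then correlated with that phenotype. The correlation must be large because the threshold requires it. The SPM text allows this.
- The SPM contrast is a pre-post change, and the mean change is then summarised from the surviving voxels. That change is inflated in the same way.

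The PET objective asks whether the infusion reduces neuroinflammation. In a single-arm study of at most 24 people, a large cluster correlation or cluster change could easily be read as evidence of a biological effect when much of its size comes from the selection rule.

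**Working it through.** **Inputs.** From the documents: n = 24 (8.1, a maximum), one arm (Protocol 3), z = 4.3 to 4.6 and pooled variance (8.2.3.2). The documents give no expected PET effect, so the true values below are assumptions: change of 0.3 to 1.0 SD, correlation of 0 to 0.5.

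**1. The plan's own threshold.** The three-dimensional Euler-characteristic term is 0.05 = R(4 ln 2)^1.5 / (2π)² × (z² − 1) exp(−z²/2). Solving for the number of resolution elements R gives 253 at z = 4.3 and 834 at z = 4.6. For an assumed 500 to 700 cm³ of grey matter, an effective smoothness of 10 to 12 mm gives z = 4.33 to 4.56, and 6 mm gives 4.84 to 4.91. The stated range is plausible. It cannot be reproduced exactly, because grey-matter volume and final image smoothness are not given. I take it as stated.

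**2. Smallest mean change that can be selected (n = 24).** With pooled variance, z applies directly and d = z/√n:
- z = 4.3: 4.3/4.899 = 0.88 SD
- z = 4.6: 4.6/4.899 = 0.94 SD

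**3. Smallest correlation that can be selected (n = 24, z = 4.3).** The documents do not fix the conversion, so I show three:
- z used as t with 22 df: 4.3/√(4.3² + 22) = 0.68
- Fisher z: tanh(4.3/√21) = 0.73
- Voxelwise t, same one-sided p (8.5 × 10⁻⁶), t(22) = 5.47: 5.47/√(5.47² + 22) = 0.76

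**4. Expected value given selection.** For a normal statistic with mean m and threshold c, E[z | z > c] = m + φ(c − m)/(1 − Φ(c − m)).

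Change, true d = 0.5: m = 0.5 × 4.899 = 2.449 and c − m = 1.851. The ratio is 0.0720/0.0321 = 2.241. So E[z] = 4.691, and 4.691/4.899 = 0.96 SD. A single such voxel is selected 3.2% of the time.

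Correlation, true ρ = 0.4, selected on that same correlation: m = atanh(0.4) × √21 = 1.941 and c − m = 2.359. The ratio is 0.02471/0.00917 = 2.694. So E[z] = 4.636, and tanh(4.636/4.583) = 0.77.

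| Assumed true change | Mean shown if selected (z = 4.3) | Ratio |
|---|---|---|
| 0.3 SD | 0.94 SD | 3.1 |
| 0.5 SD | 0.96 SD | 1.9 |
| 0.8 SD | 1.02 SD | 1.3 |
| 1.0 SD | 1.09 SD | 1.1 |

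For assumed true correlations of 0, 0.3 and 0.5, the selected values are about 0.76, 0.76 and 0.77. The number shown hardly depends on the truth.

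**5. Smooth-field check.** A simulated 512 cm³ volume (2 mm voxels, 10 mm smoothness, n = 24, z = 4.3) with a true change of 0.5 SD in a known region gave 0.93 SD in significant voxels, 0.48 SD in the same voxels in independent data, and 0.50 SD in a predefined VOI. With a true correlation of 0.4, significant voxels gave 0.76 and the predefined VOI 0.41. No voxel in the true region was significant in 46% of runs (0.5 SD) and 60% of runs (ρ = 0.4).

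**6. Correlation with a variable not used in selection.** Selecting on mean change at true d = 0.5 with pooled variance, then correlating with an outside variable of true ρ = 0, 0.3 or 0.5, gave mean r = 0.00, 0.29 and 0.49, with or without selection. The false-positive rate at ρ = 0 stayed at 5%. If each voxel's own SD were used instead, non-zero correlations would shrink (0.22 and 0.39), not grow.

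**The case against.** The strongest reply is that the plan already holds an unbiased route. The VOI analysis uses regions fixed from earlier studies and runs whatever SPM shows. PET is exploratory, Section 8.1 disclaims formal hypothesis testing, and the SPM threshold controls family-wise error for detection. All of this is true, and it limits the weight of the point. It does not remove it: error control for detection does not correct the size of what is then extracted, and no estimate or correlation is attached to the VOIs.

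A reader might also infer more than the documents support:

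- **That regional PET values exist only where SPM is significant.** This is not so; 8.2.3.1 plans VOI values separately.
- **That the PET-cytokine correlation is dropped when nothing is significant.** Nothing says this. Protocol 1.3 plans it without condition; what is missing is which PET values it uses.
- **That every extracted correlation is inflated.** Step 6 shows otherwise. The inflation arises when the selecting covariate is the variable later correlated, or one closely related to it. The text permits this but does not say it will be done.
- **That cluster effect sizes will be reported.** The extraction sentence names correlations only. Reporting a mean change from clusters is a possibility left open by the general promise in 8.1.
- **That the floors are 1.10 to 1.22 SD.** Those come from a voxelwise t with 23 df (5.41/√24 and 5.98/√24). The plan specifies pooled variance, for which 0.88 to 0.94 SD is the closer figure.

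**Conclusion.** The concern holds in this form: in the SPM stream, extraction follows significance and the extracted values feed correlations in the same subjects. This is the only stated route from PET values to a correlation. Where the selecting contrast uses the same phenotype, the result is circular: about 0.77 shown for an assumed true 0.4 at n = 24 and z = 4.3. Any mean change summarised from selected voxels would be roughly doubled at an assumed 0.5 SD, and only about 10% too high at 1.0 SD.

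The sizes rest on assumed true effects, on all 24 subjects having usable scans at both times, and on the voxel threshold. With 20 subjects the change floor rises to 4.3/√20 = 0.96 SD and the inflation is larger. Lower cluster-corrected thresholds would reduce the floors without removing the selection.

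The PET-cytokine correlation is not shown to be biased or conditional. Its defect is that its PET input is not named. For an exploratory objective this should be corrected, but it does not threaten the primary safety objective.

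**What to change.** In 8.2.3.1 and 8.2.3.2 of both documents:

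1. State that regional values are extracted for all subjects with scans from VOIs fixed before any post-treatment image analysis, whatever the SPM result. In a single-arm study this is a more usable time point than unblinding.
2. State that PET effect estimates, 95% confidence intervals and correlations, including PET-cytokine, use these VOIs.
3. Confirm that the VOI list, now described in terms of pain regulation, suits the neuroinflammation objective, or revise it.
4. Keep SPM for localisation and label values from SPM-significant clusters as descriptive.
5. Do not correlate a cluster with the variable that selected it unless the cluster is defined by leave-one-subject-out.
6. Fix the outlier rules before extraction.

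The cost is some wording and a decision on the VOI list; 8.2.3.1 already plans the VOI step. The reported effects may look smaller.
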